**6.5 Ancillary research**

Biomarkers for response to venetoclax have not yet been established for patients with AML. Response may depend on the activation of specific intracellular signaling pathways. Identification of biomarkers might help to better interpret results from clinical trials, improve the design of future trials and to identify patient groups who benefit most from this drug. Preliminary data indicate that *FLT3*-Internal Tandem Duplications and Tyrosine-Kinase Domain mutations lead to poor with response to venetoclax. Further, mutations in *TP53*, *WT1*, *PDGFRB*, *ASXL1* and *EZH2* may predict response to venetoclax (Kontro, Leukemia 2017, 31(2):301-309). Notably, a striking selective overexpression of specific *HOXA* and *HOXB* gene transcripts were detected in highly BCL-2 inhibitor sensitive AML samples. This is of specific interest since repression of *EZH2* leads to upregulation of *HOX* genes and represents a major mechanism of chemotherapy resistance in AML (Gollner, Nature Medicine, 2017;23(1):553-557). Moreover, venetoclax maintenance therapy may impact on pre-malignant clonal hematopoiesis especially when the founding clones are defined by mutations in chromatin modifiers (Shlush et al., Nature 2014 and Jeziskova et al., Int J Hematol 2015). Therefore, we will set out to study changes in the clonal composition of hematopoiesis in patients who achieved a remission.

We will apply targeted sequencing of genes implicated in AML pathogenesis, chemotherapy resistance and clonal hematopoiesis and perform RNA expression profiling for selected genes. Peripheral blood/bone marrow samples will be collected at screening, in remission and at end of cycle 2, 6 and 12 during maintenance therapy and at relapse/progression of AML according to the following schedule (Table 11):

Table 11: ancillary research – time points of collection

Timepoint / required material	Screening	CR/ CRi	during maintenance therapy			Relapse/ Progression
			End of cycle 2	End of cycle 6	End of cycle 12 = EOT	
Targeted DNA-sequencing and RNA-expression profiling of purified bone marrow (BM) blasts - 5 mL BM in EDTA Tube - 3 mL heparinized BM	x	x				x
Targeted DNA-sequencing of peripheral blood (pB) - 9 mL pB in EDTA Tube	x	x	x	x	x	x

Please ship the samples preferably from Monday – Thursday; shipment on Friday should be avoided.

Shipment Address:

Arbeitsgruppe Immunologie der MK1, Haus 66  
[name] / [name] [name]  
Medizinische Klinik und Poliklinik I  
Universitätsklinikum Carl Gustav Carus  
[name]

Goals of the ancillary research project are.

- 1) To determine biomarkers for response and mechanisms of resistance to the combination of venetoclax plus cytarabine based chemotherapy
- 2) To display the course of minimal residual disease
- 3) To test if changes in the clonal composition of hematopoiesis of patients occur during maintenance therapy

## 6.6 Subject identification and registration

Each subject who signs a consent form for the study and starts any screening procedure will be assigned a unique 6-digit number during the screening period. The first 3 digits are site specific; the remaining 3 digits are subject specific and allocated in a sequential order of subjects starting

the screening period. This screening number will be entered into the eCRF regardless of whether the subject is actually treated with study drug.

On day 1, after completion of screening procedures and prior to first dose of venetoclax, the inclusion and exclusion criteria must be checked. If eligibility is confirmed, the patient will be enrolled in the trial and treatment can be started.

If eligibility cannot be confirmed, the respective patient will be defined as screening failure.

The full patient ID number for trial is composed like this:

### **RELAX – CCC – PP – E1/2**

RELAX	prefix labeling patient number as belonging to the RELAX trial
CCC	three digits for local trial center (Kliniknummer)
PP	two digits for patient screening number
E1/2	indicating the enrolment in phase 1 / phase 2

## **7 Safety reporting**

### **7.1 Definition of adverse events and adverse reactions**

#### **7.1.1 Adverse Event (AE)**

An **adverse event** is any untoward medical occurrence in a subject or clinical investigation subject administered a pharmaceutical product and which does not necessarily have to have a causal relationship with this treatment.

An AE can therefore be any unfavourable and unintended sign (including an abnormal laboratory finding), symptom, or disease temporally associated with the use of a medicinal product as part of a clinical study, whether or not related to the medicinal product. Adverse events are to be recorded regardless of their relationship to the study intervention. With respect to intensity, AEs are classified according to the CTCAE classification V5.0.

#### Protocol-specific clarifications to this definition:

- Abnormal laboratory values should be evaluated by investigator for clinical significance and do not have to be documented as an AE if they are “not clinically significant”. They are to be documented in the database on the laboratory values eCRF form only.
- In order to monitor the safety of the trial participants throughout the trial, AEs need to be documented from first dose of venetoclax until 28 days after the last dose of venetoclax administered in the context of this trial.

- A pathological finding, improved or unchanged in comparison to baseline, does not constitute an AE.
- Symptoms of the disease under study should not be classified as AEs as long as they are within the normal day-to-day fluctuation. Worsening of the underlying disease (relapse or disease progression) or of other preexisting conditions will be recorded as an AE.

Adverse events are classified as either serious or non-serious:

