Statistical Considerations	
The phase I part will be conducted according to the enhanced algorithms of a 3+3H design (Ji et al. J Clin Oncol 2013).
 
The phase II part will be performed as single stage study adopting the A'Hern design (A'Hern Stat Med 2001). The phase II part of the trial will test the null hypothesis that the CR/CRi rate is <math>\leq 45\%</math>. This benchmark for the CR/CRi rate was selected based on literature review of trials for this patient population. The primary efficacy analysis the CR/CRi rate will be calculated by the number of observed CR's/CRi divided by the total number of patients in the phase II full analysis set. We expect a CR/CRi rate of 65% with the combination treatment. This expectation is based on CR/CRi rates reported for the combination of venetoclax and demethylating agents in patients with de novo AML being around 70% (DiNardo ASH 2015, Pollyea ASCO 2016). The null hypothesis will be tested with the one-sample exact binomial test with a one-sided type one error probability of 5% and a power of 80%. Given 25 CR/CRis observed among the 42 patients treated at the MTD the null hypothesis will be rejected.

Anticipated Duration	
Entire Trial
 
First patient in to last patient out (months): 48 months
 
Recruitment period (months): 24 months
 
Follow-up period: 24 months after enrolment of last patient
 
Follow-up period per patient: minimum 24 months after study enrolment
 
AE reporting period: day 1 of V-MAC until 28 days after end of venetoclax treatment

Ancillary Research	
Biomarkers for response to venetoclax have not yet been established for patients with AML. Response may depend on the activation of specific intracellular signaling pathways. Identification of biomarkers might help to better interpret results from clinical trials, improve the design of future trials and to identify patient groups who benefit most from this drug. Moreover, venetoclax maintenance therapy may impact on pre-malignant clonal hematopoiesis especially when the founding clones are defined by mutations in chromatin modifiers (Shlush et al., Nature 2014 and Jeziskova et al., Int J Hematol 2015).

Therefore, we will set out to study changes in the clonal composition of hematopoiesis in patients who achieved a remission.

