### **3.2 Definition and determination of the maximum tolerated dose**

The combination of cytarabine and mitoxantrone plus venetoclax will be evaluated for tolerability in a 3+3 design. In a 3+3 design, three patients will form a cohort. Each cohort will receive a higher cumulative dose of cytarabine in the predefined dose escalation steps (see Table 1) in combination with a fixed dose of mitoxantrone and venetoclax. If one patient in a cohort experiences a DLT, the cohort will be expanded to 6 patients. If 0/3 or 1/6 patients in a cohort experience a DLT, the next dose escalation cohort will be opened. If two or more patients in a cohort experience a DLT, the next lower cytarabine dose will be defined as MTD. In case of  $\geq 2$  DLTs at the dose level 1, level -1 will be used as fallback option. In case of 0 or 1 DLT in the highest dose level, the MTD was not reached and this dose level will be defined as recommended phase-2 dose (RP2D).

The DLT evaluation period is defined as the first 28 days from the start of venetoclax treatment. If a patient has not recovered peripheral blood counts by day 28, the DLT evaluation period for hematologic toxicities will be extended until day 45 from start of V-MAC.

Note: If a DLT of TLS occurs during the lead-in period, it may affect dosing decisions in the ramp up period.

A DLT is defined as any of the following occurring events of a dose level and regarded to be probably or definitely related to venetoclax. The assessment is based on the question whether there was a “reasonable causal relationship” to venetoclax. Possible answers are “possible” or “unlikely”. An assessment of “unlikely” would include the existence of a clear alternative explanation, e.g. mechanical bleeding at surgical site or non-plausibility, e.g. the subject is struck by an automobile when there is no indication that the drug caused disorientation that may have caused the event.

Certain adverse events are likely to occur in the study population (AML) independent of drug exposure. Such events include known consequences of the underlying disease under

investigation (e.g. symptoms, disease progression). These events are listed in [Appendix 5](#). If not mentioned in Appendix, events with no reasonable causal relationship to venetoclax will not be considered as DLT. On the other hand, unlikely related events with unusually high occurrence during the trial could be considered DLT if agreed by the steering committee.

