## 5 Study treatment

### 5.1 Investigational medicinal product (IMP) venetoclax

#### 5.1.1 Description of the IMP

The study drug provided is venetoclax. The study drug will be supplied as 10mg, 50 mg and 100 mg film coated tablets in blisters or bottles. See current Investigator's Brochure for further characteristics, mechanism of action, preclinical activity, side effects, pharmacokinetics and results of clinical trials.

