## 5.2 Cytarabine

Commercially available cytarabine will be given and provided locally.

For information on the formulation, packaging, and handling of cytarabine see the summary of product characteristics (SmPC) for cytarabine as used in standard practice.

Cytarabine will be defined as Investigational medicinal product (IMP) for Phase I/ Escalation Phase only, in Phase II/ Expansion Phase, it will be given as concomitant medication.

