## 6 Study procedures

### 6.1 Study flowcharts and visit schedules

Table 9: Visit schedule Escalation and Expansion part

	V0 – Screening	Enrolment	V1	V2	V3	V4	V5	V6	V7	V8 – Remission Assessment i	Premature EOS	Post-study Follow-up k
Study – Day	-14 to -1	1 (predose)	1	2-6 daily	7	9	11	18	22	28-45 (all patients)	7-14 days after last dose for safety	Every 3 months
Informed Consent	x											
Check Inclusion/Exclusion Criteria		x										
Demographics, Medical/Treatment History	x											
Physical exam, ECOG, Vital Signs l	x		x		x			x		x	x	
body weight and height m	x		x							x	x	
Full Blood Count a	x		x	x	x	x	x	x	x	x	x	
Chemistry and Coagulation b,c	x		x		x	x	x	x	x	x	x	
TLS chemistry tests d			x	x								
Bone marrow assessment e	x							x f		x	x if progress	
Material shipment for central Review g	x							x		x	x if progress	
HIV-Test	x											
Virus diagnostics n	x											
β-HCG pregnancy test h	x											
ancillary research material o	x									x	x if progress	
Adverse Events			Continuously starting from day 1 until 28 days after last dose of venetoclax									
Concomitant Medication			Continuously starting from day 1 until 28 days after last dose of venetoclax									
Disease status & Survival												x

- a Blood count (hemoglobin, hematocrit, white blood cells, platelets) incl. differential - for screening and remission assessment microscopic differential is required for peripheral blasts. In addition, blood count should be done 3x/week until hematologic recovery and as often as necessary in the opinion of the treating physician
- b Determination of: sodium, potassium, calcium, creatinine, urea, ALAT (GPT), ASAT (GOT), LDH, alkaline phosphatase, bilirubin, total protein, albumin, uric acid, INR, aPTT, fibrinogen.

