## 6.3 Assessment of safety

Regular safety assessment will ensure that patients have no or minimal study related risk. Safety evaluations will include results of physical examinations (including neurological disorders), vital signs (blood pressure, heart frequency, temperature), AEs, concomitant medications, and abnormal laboratory tests.

The following parameters will be used for safety assessment:

- Rate of early deaths (within 14 and 30 days) and induction deaths (until day 60 or until the beginning of next treatment – whichever occurs first)
- Incidence of serious infectious complications (Grades 3-5 CTCAE V5.0)

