## **7.3 Reporting of SAEs and SARs**

### **7.3.1 Reporting responsibilities of the investigator**

#### **SAEs**

All SAEs should be immediately reported by the investigator, i.e. within 24 hours after becoming aware of an event, which meets the definition of a SAE in 7.1.2. SAEs need to be reported to the sponsor's safety desk from day 1 of study treatment (= enrolment) until 28 days after last administration of study drug, regardless its causal relationship to the study drug.

If relevant information is missing at the time of the initial SAE report, the reporter should provide it in follow-up SAE report(s). Important follow-up information must also be reported as soon as they are available within 24 hours to the sponsor's safety desk. A follow-up report should contain new, updated or corrected information. The follow-up report should describe whether the event has resolved or continues, if and how it was treated including documentation of all supportive actions taken. Prompt notification (i.e. within 24h) of SAEs by the investigator to the sponsor's safety desk for SAE receipt is essential so that the legal obligations and ethical responsibilities towards the safety of the subjects are met. The investigator will comply with the applicable local regulatory requirements related to the reporting of SAE to CAs and ECs.

The investigator has to report any SAE immediately after the awareness in the AE/SAE section of the eCRF with all known and relevant information and has to sign and send the SAE page. The RELAX Safety Desk will be informed via Email about the occurrence of the SAE automatically.

In case the database does not work, the SAE has to be reported by fax or Email using the SAE form (sample in ISF).

RELAX Safety Desk, Medizinische Fakultät der TU Dresden, [contact], E-mail: [[contact]](mailto:[contact]) , [contact]

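### Adverse event collection, tied to the last venetoclax dose, closes before the day-45 observation limit, and closes earliest in patients who stop venetoclax early

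*Protocol*

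**What the plan says.** **AE window.** Section 7.1.1 sets the rule: "AEs need to be documented from first dose of venetoclax until 28 days after the last dose of venetoclax administered". The Synopsis (Anticipated Duration) gives "AE reporting period: day 1 of V-MAC until 28 days after end of venetoclax treatment", and Table 9 in section 6.1 has "Continuously starting from day 1 until 28 days after last dose of venetoclax". Section 7.2 repeats the rule.

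**SAE window.** Section 7.3.1 runs "from day 1 of study treatment (= enrolment) until 28 days after last administration of study drug". Section 5.1.1 identifies the term: "The study drug provided is venetoclax". Table 10 (maintenance) counts instead from the last dose of IMP. Section 5.2 adds: "Cytarabine will be defined as Investigational medicinal product (IMP) for Phase I/ Escalation Phase only".

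**Length of venetoclax treatment.** Section 5.4.1 limits it to 14 days, or 10 days at level -1, except in maintenance.

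**Observation limit.** Under section 3.2, if counts have not recovered by day 28, "the DLT evaluation period for hematologic toxicities will be extended until day 45 from start of V-MAC". Section 6.4.2.2 puts the remission assessment between days 28 and 45, and section 3.7 names day 45 as the minimum time on study without maintenance. Under section 4.4.1, patients taken off venetoclax, including for a DLT, stay in the trial and complete every visit up to V8.

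**The concern.** The safety clock starts from the last venetoclax dose, whereas the observation clock starts from day 1. The two do not meet, and nothing in the protocol carries AE or SAE collection on to V8.

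The uncovered days are late days of cytopenia in patients whose counts recover slowly, when infection and bleeding are to be expected. Tolerability is a secondary endpoint, and section 6.3 names grade 3-5 infection as a safety parameter. Sections 8.1.5.3 and 8.2.7.2 report AEs as counts and percentages among all patients exposed to venetoclax. A patient stopped early for toxicity stays in that denominator but is observed for the shortest time. The resulting bias is downward and falls on the patients with the poorest tolerance. Later analysis cannot restore events that were never collected.

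**Working it through.** **Inputs.** AE/SAE end = last venetoclax day + 28 (sections 7.1.1, 7.2, 7.3.1). Last planned venetoclax day = 14, or 10 at level -1 (section 5.4.1). Observation limit = day 45 (sections 3.2, 3.7, 6.4.2.2). The protocol gives no calendar day for the end of AE collection, so there is no stated figure to reproduce.

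**Formula.** Let d be the last venetoclax day. Collection ends on day d + 28, and the uncovered days are 45 - (d + 28) = 17 - d.

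| Last venetoclax day | Collection ends | Uncovered days to day 45 |
|---|---|---|
| 14 (full course, levels 1-3) | 42 | 3 |
| 12 | 40 | 5 |
| 10 (full course, level -1) | 38 | 7 |
| 7 | 35 | 10 |
| 4 | 32 | 13 |
| 1 | 29 | 16 |

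To reach day 45, the last dose would have to fall on day 45 - 28 = 17 or later, which the schedule does not allow outside maintenance.

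**DLT-free evaluable patients, levels 1-3.** Section 3.2.1 requires at least 3800 mg of venetoclax. The ramp-up gives 50 + 100 + 200 = 350 mg by day 3, then 400 mg daily. The total is 350 + 8 × 400 = 3550 mg on day 11 and 350 + 9 × 400 = 3950 mg on day 12. The threshold is therefore met on day 12 at the earliest, collection ends on day 40 or later, and the gap is at most 5 days.

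**Does the 28-day DLT window stay covered?** Yes. The earliest possible end is 1 + 28 = day 29.

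**Would counting from cytarabine help?** Its last planned day is 6 at levels 2 and 3, and 10 at levels -1 and 1. That gives day 34 or day 38, both short of day 45. It matters only if venetoclax stops first. Suppose, as an assumption, that venetoclax stops on day 3 and cytarabine runs to day 10 at level 1. Collection then ends on day 31, which is 31 - 10 = 21 days after the last dose of an IMP.

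**The case against.** The strongest defence is that 28 days after the last dose of the investigational drug is a coherent rule, applied almost uniformly, and that after a full course it falls only 3 days short. A patient who recovers by day 42 can have V8 inside the window. A temporary interruption followed by resumption does not move the end date to the interruption. All of this stands and limits the weight of the point. It does not help the patient who stops permanently and early.

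Four stronger readings are tempting, and the documents do not support them.

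- **Dose decisions rest on truncated data.** Non-hematologic DLTs and clinical TLS use the 28-day window, which is always covered. The extension to day 45 concerns hematologic toxicity only, and that is read from blood counts (three times weekly until recovery, and at V8) and from marrow. An early stopper in phase I either has a DLT and counts, or is replaced for insufficient treatment (section 4.4.2).
- **Deaths to day 60 are lost.** Section 6.3 does count "induction deaths (until day 60 or until the beginning of next treatment" and so on, but this is a mortality count, and survival follow-up runs for at least 24 months. Only the SAE report behind a death after the cut-off is not required.
- **Dose levels cannot be compared.** Levels 1, 2 and 3 plan the same 14-day course and hence the same window. Only the fallback level -1 differs, by 4 days.
- **The rule is ambiguous for maintenance patients.** Section 7.1.1 counts from the last venetoclax dose given within the trial, and Table 10 lists AEs at the maintenance pre-visit. That is one workable rule.

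**Conclusion.** The point holds as a gap in clinical AE and SAE collection for patients without maintenance: 3 days after a full course, 7 at level -1, at most 5 in DLT-free evaluable patients at levels 1-3, and up to 16 after an early permanent stop. It can bias the descriptive AE incidence and the grade 3-5 infection count downward. It does not threaten the MTD, the CR/CRi rate or the mortality counts. It should be fixed, but the trial's main conclusions do not depend on it.

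These figures rest on two assumptions. First, the patient is observed to day 45; where V8 falls earlier, the gap up to V8 is shorter or absent. Second, day 45 is counted with the first venetoclax dose as day 1; if it means 45 days after day 1, every gap is one day longer. The number of patients affected cannot be derived from the protocol, because it gives no expected rate of early discontinuation or late recovery.

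**What to change.** In the Synopsis (Anticipated Duration), Table 9, and sections 7.1.1, 7.2 and 7.3.1, define the AE and SAE window as day 1 until the later of:

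- V8/day 45, and
- 28 days after the last dose of venetoclax or, in phase I, of the last IMP, including cytarabine.

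Continue collection through maintenance where it is given. Use one term throughout, and align the reference to IMP in Table 10 with it.

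The sponsor should say whether the first limit is the V8 visit itself or a fixed day 45. A fixed day gives every patient the same minimum window, but needs a short contact when V8 has taken place earlier.

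The cost is a wording change in the protocol and eCRF guidance and a few more days of AE entry, largely at a visit patients already attend. No procedures or patients are added.

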### 7.1.2 Serious Adverse Event (SAE)

A **Serious Adverse Event** is any untoward medical occurrence that at any dose:

- results in death,
- is life threatening,
- results in persistent or significant disability/incapacity,
- requires inpatient hospitalization or prolongation of existing hospitalization,
- is a congenital anomaly or birth defect,
- is another medically important event (that may require medical treatment to avoid one of the above-mentioned conditions).

